In 2013, the InfraScanner 2000™ was introduced, prompting our group to validate it in a consecutive series of 500 head injury patients who obtained a head CT scan at Duke University Hospital (DUH). For all patients with CT-proven bleeds (n=104), irrespective of size, initial NIR scans localized the bleed to the appropriate quadrant with a sensitivity of 86% and specificity of 96% compared to a CT scan. For extra-axial bleeds >3.5ml, sensitivity and specificity were 94% and 96%, respectively. For longitudinal serial rescans with the NIR, sensitivity was 89% (<4 days from injury: sensitivity=99%) and specificity was 96%. The device demonstrated 100% sensitivity for all patients requiring craniectomy or craniotomy.

Since the DUH study, our group initiated a study of 684 TBI patients at Mbarara Regional Referral Hospital (MRRH) in Uganda using the InfraScanner 2000™. For all patients with CT-proven bleeds (n=180), irrespective of size, initial NIR scans localized the bleed to the appropriate quadrant with a sensitivity of 89% and specificity of 38% compared to a CT scan. These findings greatly differ from the DUH data set, prompting our team to conduct a secondary analysis of the MRRH data. We found evidence to suggest that skin tone variance, among other patient characteristics, affects the accuracy of the near-infrared-based device.

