A prospective cohort study is to be conducted at the MRRH Division of Neurosurgery and Mayanja Memorial Hospital (MMH) from May 2024 until May 2025 or until our sample size has been met. Prior to the study, approval from the following institutions and administrations will occur; Duke University IRB approval, Mbarara University of Science and Technology (MUST) IRB approval, Uganda National Council for Science and Technology (UNCST) approval, and administrative approval from both hospitals will be collected.

Methods & Procedures

When applicable (conscious patient and/or family or legally authorized representative (LAR), the study will be introduced to the patient and relevant parties before the research team approaches the patient. While head trauma frequently results in impaired cognition and/or consciousness, and due to the urgency of these circumstances, patients are often not accompanied by kin, whenever appropriate, the purpose of the research and the procedure will be explained in detail using an IRB-approved verbal consent “script”, with all questions answered to the patient’s and/or representative’s satisfaction.

Upon presentation to the casualty unit at MRRH or MMH and/or within 30 minutes prior to or following a CT scan, the study team will approach the patient or the patient’s LAR for permission to scan the patient’s cranium with the InfraScanner 2500™ (Image A). If permission is granted, the study team member will sequentially measure the optical absorption for each of the 8 quadrants of the scalp (frontal, temporal, parietal, and occipital bilaterally) (Image B). The device is engineered such that the light emitter and receiver are spaced 4 cm apart, allowing the light’s intensity to be measured between adjacent light guides (Image C). Parting combs will be used to help access the scalp on patients with hair that prevents the fiberoptic tips from direct contact with the scalp. A laminated swatch displaying Monk Skin Tone Orbs will be used for later analysis of skin tone on the Monk Skin Tone Scale (Image

D).²⁶ This entire procedure, including greeting, scanning the patient, should take <10 minutes. Basic demographics, neuro exam, and InfraScanner 2500™ data will be entered into REDCap (Appendix A).

The collection period for each research subject concludes within 30 days following his or her initial consent, patient or LAR decision to withdraw from further participation, hospital discharge, or patient death, whichever occurs first.

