6. **Eligibility:** Any patient aged 12 and up who presents to Mbarara Regional Referral Hospital (MRRH) or Mayanja Memorial Hospital (MMH) with suspected head trauma, who is able to or who has a LAR who is able to consent in English, Runyankole, or Luganda will be considered for this study. After being made aware of the study by a physician directly caring for the patient and agreeing to hear more about the study, the prospective participant and/or the participant's LAR will be approached.
7. **Exclusion:** Patients for which wounds to their head are too large to properly use the InfraScanner 2500™ will be excluded from this study. Patients will also be excluded if hair cannot be appropriately parted to allow for the fiberoptic tips of the device to make direct contact with the scalp. Patients for whom it is not possible to obtain an Infrascan within 30 minutes of their CT imaging will also be excluded from the study.
8. **Subject Recruitment and Compensation:** Potential research participants will be approached by the research team only if given permission by the physician in charge of the patient's care after he or she has informed the patient and/or the patient's LAR of the research and received a verbal agreement from the patient and/or LAR to hear more about the research study. Each participant will be compensated UGX 15,000 (\$4) for participation in this study. The study personnel will be trained in the consent process and will make it abundantly clear that agreement or refusal to participate in the study will not influence the patient's care in any way.

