9. **Consent Process:** After being made aware of the study by a physician directly caring for the patient and agreeing to hear more about the study, the prospective participant and/or the participant's LAR will be approached. Upon admission to MRRH for suspected head trauma, the patient's physician will introduce the patient or the patient's legally authorized representative to the presence of the study. If the consenting party agrees to hear about the study, the study coordinator or research assistant will greet the patient and speak with the patient and/or legally authorized representative, thoroughly describing the protocol and reason for the study. All consenting study personnel will be trained in the consent process and will provide ample reassurance to the patient or consenting party that the decision to participate will not, in any way, affect his/her medical care. Care will be taken to thoroughly answer all questions prior to obtaining final consent. The patient and/or legally authorized representative will be clearly informed that the research protocol is completely optional, that participation will not affect the treatment they receive, and that, should they give consent, they are free to withdraw from the study at any time. Participants will have the opportunity to decide on their involvement in the study up until they receive their first CT scan at either hospital, provided this decision is made before the end of the 30-minute post-scan window. If they do not consent

before their first CT scan and outside this 30-minute timeframe, they will be ineligible for inclusion in the study. Participants will be afforded time to withdraw from the study up until 30 days following initial consent or are discharged from medical care. The consent process will occur in the casualty unit at MRRH and MMH or the MRRH intensive care unit (ICU). The study team will be readily available to the patient, legally authorized representative, and/or patient's relatives throughout the study for any questions or concerns they may have.

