Any patient aged 12 and up who presents to MRRH or MMH with a suspected head trauma scan will be considered for this study. Based on previously reported data, we expect that true hematoma will be present in approximately 46% of participants overall.²⁸

b) Standard of comparison:

All patients entered into the trial will have undergone one cranial CT scan prior to enrollment and will be consented for the study. All patients enrolled will undergo one cranial scan using the InfraScanner 2500™ within 30 minutes of the CT scan. Patients and care providers will be blinded to the results of InfraScanner 2500™. The standard for comparison will be determined as follows. A CT result that is positive for hematoma will be considered a true positive, and a CT result that is negative for hematoma will be considered a true negative.

Definitions of Sensitivity, Specificity, False Positive, False Negative:

Let T^+ denote the event that the test is positive for hematoma, and D^+ denote the event that a hematoma is present. Sensitivity, $P(T^+/D^+)$, will be defined for each patient's InfraScanner results as the probability that a true hematoma, as determined by a CT scan, will be detected. Similarly, let T^- denote the event that the test is negative for hematoma and D^- denote the event that a hematoma is not present.²⁹ Specificity, $P(T^-/D^-)$, will be defined as the probability of being negative for a hematoma on the InfraScanner 2500™ scan within 30 minutes of CT given the patient has no hematoma present.

The false positive rate will be defined as $P_{F+} = P(D^-/T^+) = P(T^+/D^-)[1-P(D^+)]/P(T^+)$. Similarly, the false negative rate will be defined as $P_{F-} = P(D^+/T^-) = [1-P(T^+/D^+)]P(D^+)/[1-P(T^+)]$. Estimates for the false positive and false negative rates will be provided for a range of values for the prevalence of hematomas.

c)  Sample Size

Computation of the required number of patients is based on estimating the sensitivity of each method to within at most +/- 0.099 with 95% confidence. The 95% confidence interval for the sensitivity based on previous findings,²⁸ and the sample size calculator provided.^{29,30}

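### Timing of enrolment relative to CT is contradictory, and with a physician gate, no consecutive rule and no screening log, entry of patients approached after CT can depend on the CT result.

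*Combined protocol and SAP*

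**What the plan says.** **Timing.** Section 15(b) says "All patients entered into the trial will have undergone one cranial CT scan prior to enrollment and will be consented for the study". Section 5 (Methods & Procedures) sets the approach at "Upon presentation to the casualty unit at MRRH or MMH and/or within 30 minutes prior to or following a CT scan". Section 9 says "Participants will have the opportunity to decide on their involvement in the study up until they receive their first CT scan at either hospital", and extends this to the end of the 30 minutes after the scan.

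**Who is approached.** Section 8: "Potential research participants will be approached by the research team only if given permission by the physician in charge of the patient's care". Section 9 says that the physician will introduce the study on admission for suspected head trauma, but names MRRH only. Sections 13 and 15(b) mask care providers to the device result; nothing masks them to the CT. Under Section 10, impaired patients can take part only through a representative, and Section 5 notes that patients often arrive without relatives.

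**Sampling rule.** Section 15(a) says that eligible patients "will be considered for this study"; no section requires all of them, in sequence, to be offered entry. By contrast, the Background describes the Duke work as an effort to "validate it in a consecutive series of 500 head injury patients".

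**Records.** Appendix A has fields for why a CT was not done and whether hair blocked the scalp. It has none for patients not introduced, permission withheld, refusal or no representative. The limitations in Section 18 mention only injuries that prevent use of the device.

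**Estimands.** The primary objective includes the false positive and false negative rates, which Section 15 defines as P(D-|T+) and P(D+|T-). It adds: "Estimates for the false positive and false negative rates will be provided for a range of values for the prevalence of hematomas". It does not list the values.

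**The concern.** In a diagnostic accuracy study, the decision to enter a patient should not depend on the reference standard. Here, under the Section 15(b) wording, the CT is done before enrolment, and the person who decides whether the team may approach is free to know its result. CT-negative patients who are well could leave without being introduced, or urgent bleeds could be passed over. The direction cannot be predicted, and without a log it could not be seen afterwards.

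Two things could move. The first is the share of CT-positive patients in the sample, which enters both primary error rates directly. The second is the mix of bleeds, which acts on sensitivity itself. Aim 1 concerns use as a triage tool, so the probability of a bleed after a negative scan is a figure that users will look at closely. Specificity was 96% at Duke and 38% at MRRH with the previous model. If the new result differs again, a reader will want to know whether case selection contributed.

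One loss needs no knowledge of the CT: impaired patients without a representative cannot enter, and they too go uncounted.

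**Working it through.** **1. The plan's own accrual figures.** Section 15(c) gives 171 patients before dropout and 171/0.95 = 180 after. It expects 50% of TBI patients to have a CT, so 360 × 0.50 = 180. The 360 therefore leaves no room for eligible CT patients who are not introduced, not permitted, refuse or have no representative; the 5% is for dropout. Nothing planned would show whether capture was complete.

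**2. Effect of a shift in the share of bleeds.** Inputs: share 0.46 (Section 15(a)); sensitivity Se = 0.89 and specificity Sp = 0.38 (Background, earlier MRRH study with the InfraScanner 2000). The selection ratio k is assumed: CT-positive patients are enrolled k times as often as CT-negative ones.

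- Enrolled share: p = 0.46k / (0.46k + 0.54)
- P(D-|T+) = (1-Sp)(1-p) / [(1-Sp)(1-p) + Se·p]
- P(D+|T-) = (1-Se)p / [(1-Se)p + Sp(1-p)]

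With k = 1, P(D-|T+) = 0.3348/(0.3348 + 0.4094) = 45.0% and P(D+|T-) = 0.0506/(0.0506 + 0.2052) = 19.8%.

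With k = 2, p = 0.92/1.46 = 0.630. P(D-|T+) = 0.2293/(0.2293 + 0.5608) = 29.0% and P(D+|T-) = 0.0693/(0.0693 + 0.1405) = 33.0%.

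With k = 0.5, p = 0.23/0.77 = 0.299. P(D-|T+) = 0.4348/(0.4348 + 0.2658) = 62.1% and P(D+|T-) = 0.0329/(0.0329 + 0.2665) = 11.0%.

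| k | Enrolled share | P(D-\|T+) | P(D+\|T-) |
|---|---|---|---|
| 0.5 | 29.9% | 62.1% | 11.0% |
| 1 | 46.0% | 45.0% | 19.8% |
| 1.5 | 56.1% | 35.3% | 27.0% |
| 2 | 63.0% | 29.0% | 33.0% |

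Here k is a ratio of frequencies, not of odds. If CT-negative patients were enrolled 50% of the time (assumed), doubling the odds would mean 67% against 50%, so k = 1.33. The enrolled share would be 0.6133/1.1533 = 53.2%, P(D-|T+) 38.0% and P(D+|T-) 24.7%.

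**3. Effect of a shift in bleed mix.** The Duke series gives sensitivity 86% for all bleeds and 94% for extra-axial bleeds above 3.5 ml, with specificity 96% for both. At a fixed 46% share:

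- Se 0.86: P(D+|T-) = 0.0644/(0.0644 + 0.5184) = 11.1%
- Se 0.94: P(D+|T-) = 0.0276/(0.0276 + 0.5184) = 5.1%

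This is an outer case, since it replaces the whole mix by the easier group. It does show that the rate can halve with prevalence unchanged, which a table over prevalences would not reveal.

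**The case against.** The strongest reply has five parts.

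- **Enrolment is not uniformly after CT.** A reader of Section 15(b) alone might infer that it is. Sections 5 and 9 do not support that, since both allow approach or consent before CT. What stands is a contradiction to be reconciled, and a risk confined to patients approached after CT.
- **Physicians are told to introduce patients.** Section 9 is unconditional and tied to admission, not to the CT. It names MRRH only, however, and Section 8 still requires permission before any approach.
- **Selection on CT is not shown.** A reader might infer that referral determines the share and mix of bleeds. No section says that permission depends on the CT, or even that the CT has been read within the 30 minutes. This stands: it is a possibility that the plan leaves open.
- **Prevalence is already handled.** Reporting both rates over a range answers a shift in share, provided sensitivity and specificity are unaffected. But the range is unspecified, and no data would say which value applies at these hospitals. The planned analyses by detection limits, type and location will describe the enrolled mix, not how it differs from the mix of those left out.
- **The mix effect may be small.** Even the full 8-point gap between 86% and 94% lies within the planned ±9.9 points. That is fair as to size, but a confidence interval does not cover selection bias.

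**Conclusion.** The point holds as a cheap improvement. The sections disagree on when enrolment occurs relative to CT. Approach depends on a physician who is not masked to CT. There is no explicit consecutive rule for both hospitals and no count of eligible patients who did not enter.

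Under twofold selection in either direction, P(D+|T-) would move from 19.8% to 33.0% or 11.0%, and P(D-|T+) from 45.0% to 29.0% or 62.1%. Milder selection gives smaller shifts. These figures rest on an assumed selection ratio, the planned 46% share, and accuracy figures from the previous model held fixed. They show how far the rates could move, not how far they will.

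It might seem to follow that the headline rates should be recalculated at the prevalence among all head-trauma CTs. The documents do not support that step. It would also hold the enrolled sensitivity and specificity fixed, and it might leave the target population, which the primary objective limits to hospitalised patients. Extending the comparison to bleed mix would need size and depth readings on people who did not consent.

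**What to change.** 1. Reconcile Sections 5, 9 and 15(b) on when enrolment and consent occur relative to CT.
2. State in Section 15(b) that eligible patients with suspected head trauma who have a CT at either hospital while study staff are on duty are introduced consecutively, with permission sought before the CT result is known where possible. Extend the introduction sentence in Section 9 to MMH.
3. Keep a de-identified screening log with one line per eligible CT patient: enrolled; not introduced or not permitted; declined; no representative; outside 30 minutes. Add CT hematoma yes/no where ethics approval allows.
4. List the prevalence values for the planned range and include the log's CT-positive share among them, as a sensitivity analysis. Keep the planned enrolled-sample rates as the headline.
5. Name physician permission and missing representatives in the limitations.

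The log shows a shift in share but not in mix. Against a shift in mix, the protection is the consecutive rule and seeking permission before the result is known.

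The sample size stays at 180 and no patient procedure is added. The cost is a few sentences, a little clerical work, and ethics wording for counts of patients who did not enrol. The log has to start with enrolment, since withheld permissions and refusals may not be recoverable later.

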- 10. Subject's Capacity to Give Legally Effective Consent:** We expect that most of the subjects will be neurologically and/or cognitively impaired due to the extent of head injury, multisystem trauma, and/or medical treatments. Since this is a minimal-risk study, we will offer study participation to subjects with diminished abilities if they have a legally authorized representative. For patients with less severe injuries and those who are later hospitalized with resolving injuries, we expect subjects to be cognitively intact and capable of autonomously making decisions about their routine medical care. For such patients, they can consent without the need for a legally authorized representative. The study will also be offered to patients 12 years of age and older. For patients younger than 18 years, we will obtain assent from the subject, when he or she is cognitively able, and consent from their legal representatives or parents.
- 11. Study Interventions:** As described above, within 30 minutes of each CT scan, the study team will scan the study subject's cranium with the InfraScanner 2500™. The previous model, InfraScanner 2000™ (**Image A**), shows the size of the noninvasive fiberoptic tips that make contact with the scalp. The InfraScanner 2500™ has an improved algorithm embedded in the new software, while the hardware mechanisms of detection remain unchanged between the InfraScanner 2000™ and InfraScanner 2500™ models. The study team member will use the device to sequentially emit light through fiber optic light guides rested upon the patient's scalp so that near-infrared light can be emitted in each of the quadrants (**Image B**). The device is engineered such that the light emitter and receiver are spaced 4 cm apart, allowing the light's intensity to be measured between adjacent light guides (**Image C**). This entire procedure should take <10 minutes.

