- 13. Risk/Benefit Assessment:** There are no known health risks associated with the use of NIR. All data obtained with the Infrascanner 2500™ will be blinded from physicians participating in the care of study patients to ensure there is no deviation from the standard of care. While there are neither any specific direct clinical benefits to the research participant through participation in this study, the involvement may provide significant future benefits to the community and enhance TBI care in Uganda and LMICs globally. This contribution to advancing medical knowledge and improving TBI management strategies underscores the importance of participation. Participants will be compensated approximately UGX 15,000 (\$4 USD) for their contribution to this valuable research effort.
- 14. Costs to the Subject:** No additional costs to the patient will be incurred as a result of this add-on research protocol.

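### No section keeps the CT result from the InfraScanner operator, and the sections disagree on whether a patient consented and scanned before CT is eligible

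*Combined protocol and SAP*

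**What the plan says.** **Masking.** Section 15 b) (Standard of comparison) states: "Patients and care providers will be blinded to the results of InfraScanner" 2500. Section 13 says that device data "will be blinded from physicians participating in the care of study patients to ensure there is no deviation from the standard of care". Both statements concern the device result, and the purpose given in Section 13 is clinical. Neither mentions the CT result.

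**Order.** Section 15 b) states: "All patients entered into the trial will have undergone one cranial CT scan prior to enrollment". Section 5 (Methods & Procedures) has the team ask permission to scan "Upon presentation to the casualty unit at MRRH or MMH and/or within 30 minutes prior to or following a CT scan". In Section 9 the treating physician introduces the study "Upon admission to MRRH for suspected head trauma". The section continues: "Participants will have the opportunity to decide on their involvement in the study up until they receive their first CT scan at either hospital", and lets the decision run to the end of the 30 minutes after that scan. Section 7 excludes anyone who cannot have the device scan within 30 minutes of CT.

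**Number of scans.** Section 15 b) plans a single device scan: "All patients enrolled will undergo one cranial scan using the InfraScanner" 2500. Section 11 calls for a device scan "within 30 minutes of each CT scan". Appendix A has fields for the first device scan only.

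**The concern.** The primary objective is sensitivity and specificity against CT. An accuracy study needs masking in both directions: the reference standard read without the index test, and the index test done without the reference standard. The plan addresses the first, at least for those giving care, and is silent on the second.

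An operator who knows where CT shows blood, or that it shows none, could place the probe or part the hair differently. A hair or wound exclusion judged with CT known could change the case mix, in a direction that the documents do not settle.

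The order of CT and enrollment matters for two reasons. It decides which patients are eligible, and it decides how many device scans take place when a CT result might already be known.

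**Working it through.** The plan gives no figure on this point, so the check sets the sections side by side.

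**1. Who is masked to what.**

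| Information | Kept from | Stated? |
|---|---|---|
| Device result | Treating physicians | Yes, Section 13 |
| Device result | Patients and care providers | Yes, Section 15 b) |
| Device result | Person coding the CT fields | Not stated; a clinical CT reader may count as a care provider |
| CT result | Device operator | Not stated anywhere |
| CT result | Person judging hair and wound exclusions | Not stated anywhere |

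The only double-blind wording, in Background and Significance, describes an earlier trial of another model.

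**2. Which orders each section allows.**

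| Section | Before CT | After CT |
|---|---|---|
| 15 b) | No: CT precedes enrollment for all | Yes |
| 5 | Yes, for the approach for permission | Yes, for the approach for permission |
| 9 | Yes, for consent | Yes, for consent, to the end of the 30-minute window |
| 7 | A 30-minute limit; direction not given | Same |

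Sections 5 and 9 allow both orders, so they overlap Section 15 b) for patients approached after CT. The conflict is confined to the patient consented and scanned before CT, who is admissible under Sections 5, 7 and 9 and not under the literal wording of 15 b).

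**3. How order bears on masking.** A device scan needs consent. If CT always precedes enrollment, every device scan follows CT. Under Sections 5 and 9 some scans could come first, but no share is given. The order conflict therefore leaves open how many scans could take place with CT known.

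**4. Where discretion remains.** Section 12 fixes the scan sites, has the scanner adjust its own settings, and displays a computed result. That leaves probe contact and placement, hair parting (Section 5), and the hair and wound exclusions (Section 7). The documents do not name who judges those exclusions; the scanning team member is the natural reading.

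**5. What the data could show later.** Appendix A records CT and device scan times to the minute, so scan order can be derived for each patient. It has no field for whether the operator knew the CT result. It has a hair-access field and an open-scalp-injury field, but no field for a wound exclusion decision. One list, with one research-assistant field, holds both the device result and the CT coding, and does not say who codes CT.

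**6. Size.** An estimate of bias would need the share of scans done after CT, the share of those in which the operator knew the result, and the share of readings changed by knowing it. The documents give none of the three. Operator masking would not change the planned 171 patients with CT or the total of 180, because Section 15 c) builds these on precision, prevalence and dropout.

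**The case against.** The best reply is that the device leaves an operator little to influence. Sites are prescribed, the readout is automatic, and Appendix A stores a numeric result for each area beside the yes/no result. A CT result may also not reach the operator within 30 minutes. Most of this stands, and it limits the likely harm. It does not close the gap: a number recorded from a differently placed probe carries the same influence as the yes/no result, and the exclusions are judged by a person.

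It is also fair to say that Section 5 times the approach and not the scan, and that Section 9 allows a decision after CT as well as before. Both points narrow the order conflict to the one stated in the working; neither removes it.

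Four stronger readings are tempting and not supported:
- **That accuracy will be overstated.** Nothing shows that any reading would change, or in which direction.
- **That operators will know the CT result.** Section 16 describes continual contact between the research and treating teams about clinical status and enrollment; it does not mention CT results.
- **That the Appendix A field for why CT was not done proves enrollment before CT.** Section 15 c) expects only 50% of TBI patients to obtain CT, so the field may serve as a screening record.
- **That CT is read with the device result known.** A clinical reader is plausibly covered by the existing masking; only the person coding the CT fields is unspecified.

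**Conclusion.** The point holds in limited form. Masking is stated for the device result only, and nothing keeps CT from the operator. Section 15 b) conflicts with Sections 5 and 9 on whether a patient consented and scanned before CT is eligible, and with Section 11 on whether there is one device scan or one for each CT.

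Review bias in the primary estimates is possible, not demonstrated, and cannot be sized from the documents. The conclusion rests on two readings: that the device scan follows consent, and that the scanning team member judges the hair and wound exclusions. The matter should be corrected because the protection is inexpensive and because operator knowledge that was never recorded cannot be recovered at analysis. It is not a reason to reject the design.

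**What to change.** 1. Reconcile Sections 5, 9, 11 and 15 b) on the order of CT, consent and device scan, and on the number of device scans. Make Appendix A match.
2. Require the device result and any hair or wound exclusion decision to be entered, time-stamped and locked in REDCap before the operator sees or is told the CT result. Add one field recording whether the operator knew it, and a field for the wound exclusion decision if none exists.
3. State that whoever codes `ct_pos` and the regional CT fields does so without the InfraScanner result.
4. If both orders are kept, describe sensitivity and specificity by scan order from the times already collected, without a formal test.

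The cost is protocol wording, minor REDCap changes, and the discipline that operators do not look at CT before the scan is locked. The documents do not describe staffing, so whether that last step needs extra people is unknown. The sample size does not change.
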